### **Cardiac enzymes**

- High sensitivity troponin T ( $\text{ng}/L$ ).

### **Urinalysis**

- Urine Albumin ( $\text{mg}/L$ );
- Urine Creatinine ( $\text{mmol}/L$ );
- UACR ( $\text{mg}/\text{g}$ ;  $\text{mg}/\text{g}$  is same as  $\text{g}/\text{kg}$ );
- Results of the dipstick analysis.

### Male reproductive hormones (local protocol)

- Total testosterone (nmol/L);
- Free testosterone (pmol/L);
- Follicle-stimulating hormone (IU/L);
- Luteinizing hormone (IU/L);
- Inhibin B (ng/L).

### Semen analysis

- Sperm concentration ( $10^6$ /mL);
- Ejaculate volume (mL);
- Total sperm number ( $10^6$ /ejaculate): derived as Sperm concentration ( $10^6$ /mL)  $\times$  Ejaculate volume (mL);
- Sperm motility (%);
- Normal sperm / total sperm (%).

Data in conventional units for hematocrit, N-terminal pro-brain natriuretic peptide (NT-proBNP), and UACR [respectively %, ng/L, and g/kg] will be derived from SUPPLB dataset merged by USUBJID and LBSEQ with LB dataset (using SUPPLB.IDVARVAL to match LB.LBSEQ and QNAM; LBCVRES, QNAM.LBCVRESU, QNAM.LBCVNRLO, and QNAMLBCVNRHI to get value, unit, and normal range).

### 10.3 Vital signs

- Change from baseline to each visit up to Month 6.
- Treatment-emergent marked abnormalities.

Vital signs include systolic blood pressure (SBP; mmHg), diastolic blood pressure (DBP; mmHg), mean arterial pressure (MAP; mmHg), heart rate (bpm) and body weight (kg). MAP will be derived as  $(SBP + 2 \times DBP) / 3$ .

### 10.4 12-lead ECGs

- Change from baseline to each visit up to Month 6
- Change from pre-dose to 2 hours and 4 hours post-dose at Month 1
- Treatment-emergent marked abnormalities.

12-lead ECG parameters include heart rate (HR; bpm), PR (ms), QRS (ms), QT (ms), QTc according to Bazett's formula (QTcB; ms), QTc according to Fridericia's formula (QTcF; ms), and any morphological abnormalities as defined by the central ECG vendor.

Quantitative results (HR, PR, QRS, QT, QTcB, QTcF) will not be available for hard copy ECGs read by the central ECG vendor (only the interpretation will be available).

## 11 QUALITY OF LIFE ENDPOINTS

Using the SF-36v2 data collected at baseline and Month 6, the z-score (with reference to a US adult population [Ware 2000]) of each of the 8 domains (physical functioning, role physical, bodily pain, general health, vitality, social functioning, role emotional, mental health) and the 2 component scores (physical health, mental health) are derived at baseline and Month 6 from the 36 source items. Finally, the 8 domain z-scores and the 2 component scores are transformed to T-scores via the norm-based (50, 10) scoring [derivations are detailed in Appendix A].

The change from baseline to Month 6 of a score will be calculated as the difference (T-score at Month 6 – T-score at baseline). In the event of a missing Month 6 score (after application of the SF-36 scoring rules), the score will be left missing in the analysis.

The health transition item (much better than one year ago, somewhat better than one year ago, about the same as one year ago, somewhat worse than one year ago, much worse than one year ago) will be used without transformation. In the event of a missing Month 6 health transition item, the item will be left missing in the analysis.

The values collected during the study will be mapped to protocol visits according to the windowed times described in Table 5.

## 12 PHARMACOKINETIC ENDPOINTS

Lucerastat plasma concentrations will not be available for analysis of PK parameters until the study database is locked.

For PK analyses, values BLQ will be imputed with 0.

If a time of PK sampling is missing, no imputation will be applied.

### 12.1 Trough plasma concentration of lucerastat at each visit up to Month 6

The trough plasma concentration of lucerastat will be assessed at each visit up to Month 6 (i.e., at Months 1, 3, 5, and 6).

### 12.2 PK samples collected at Month 1 (PK profile sub-study)

A 12-hour PK profile will be obtained from subjects participating in the PK sub-study at the Month 1 visit. The following endpoints are defined:

- The area under the plasma concentration-time curve during one dosing interval ( $AUC_{\tau}$ ),
- The maximum plasma concentration ( $C_{max}$ ) during one dosing interval,
- The time to reach maximum plasma concentration ( $t_{max}$ ) during one dosing interval,
- The apparent terminal elimination half-life ( $t_{1/2}$ ).

They will be derived from the concentration-time data by the Idorsia Clinical Pharmacologist.

### 13 BIOMARKERS OF FABRY DISEASE AND LUCERASTAT MECHANISM OF ACTION

As for plasma Gb3, these data will not be available for statistical analysis until the study database is locked and the randomization code is broken.

As for plasma Gb3, the data collected at baseline and Month 6 for plasma lysoGb3 (ng/mL), GlcCer (ng/mL), LacCer (ng/mL) and urine Gb3 and lysoGb3 (both normalized to creatinine) will be used to derive their change from baseline to Month 6 as the difference (Month 6 – baseline) and also as the percent change from baseline ( $100 \times [\text{Month 6} - \text{baseline}] / \text{baseline}$ ).

Urine Gb3 and urine lysoGb3 will be normalized as follows:

- Normalized urine Gb3 ( $\mu\text{mol Gb3/mol creatinine}$ ) =  $(10^3/1024.3) \times \text{Gb3 (ng/mL)} / \text{urine creatinine (mmol/L)}$
- Normalized urine lysoGb3 ( $\text{nmol lysoGb3/mol creatinine}$ ) =  $(10^6/785.91) \times \text{lysoGb3 (ng/mL)} / \text{urine creatinine (mmol/L)}$

Values reported as BLQ will be set to the limit of quantification in the analyses. The number of values reported as BLQ by treatment group and visit will be included in the tables.

The values collected during the study will be mapped to protocol visits according to the windowed times described in [Table 5](#).

### 14 STATISTICAL ANALYSES

All available data for each subject will be used in all statistical analyses unless otherwise specified.

Data will be listed and summarized using appropriate descriptive statistics:

- Number of non-missing observations, mean, standard deviation (SD), minimum, Q1, median, Q3 and maximum for continuous variables.
- Number of events, number of censored observations and Kaplan-Meier estimates of the survival function for time-to-event variables.
- Number of non-missing observations and frequency with percentage per category for categorical variables. Denominators for percentages are the number of non-missing subjects in the pertinent analysis set and treatment group, unless otherwise specified.

The number of missing values will be displayed only if  $> 0$  and only for categorical variables, after the last category.

Absolute change from baseline is defined as: post-baseline value minus baseline value, i.e., a positive sign indicates an increase compared to baseline.

A percentage change from baseline is defined as the absolute change from baseline divided by the baseline value (if the baseline value is  $> 0$ ) and then multiplied by 100. In the event of baseline and post-baseline value both equal to 0, the ratio to baseline will be set to 1 (i.e., the percent change from baseline will be set to 0%). If baseline is equal to 0 and post-baseline value greater than 0 (infinite ratio) or if baseline greater than 0 and post-baseline equal to 0 ( $\log[\text{ratio}] = \text{minus infinity}$ ), the percent change will be missing.

Summary statistics of percentage changes will be derived from the geometric mean of the ratio to baseline transformed into a percentage change by using the transformation  $x \rightarrow (x-1) \times 100$ . The CV of the geometric mean will be derived as described in Appendix B.

In tables, column labels will be ‘Lucerastat’ and ‘Placebo’ and a total column is added in baseline disease characteristics and demography.

SAS/STAT® version 14.1 or higher will be used for all statistical analysis [SAS Institute 2015].

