### **9 EFFICACY VARIABLES**

#### **9.1 Primary efficacy endpoint**

The primary efficacy endpoint is:

- Change from baseline to Month 6 in the “modified” BPI-SF3 score of “neuropathic pain at its worst in the last 24 hours”.

Baseline and Month 6 modified BPI-SF3 scores will be obtained by averaging the weekly modified BPI-SF3 scores over the 4 weeks prior to the corresponding visit of interest (randomization visit and Month 6 visit, respectively). At least 4 of the 7 daily scores should

be non-missing to derive a valid weekly modified BPI-SF3 score and at least 3 valid weekly scores should be non-missing to derive a valid score for the relevant time period.

All available daily scores will be used to derive the scores regardless of study treatment discontinuations or introductions of new medications.

In addition, intermediate monthly modified BPI-SF3 scores from Month 1 to Month 5 (used in sensitivity and supportive analyses) will be derived with the same validity conditions.

The selection of daily scores over 4 weeks for each time point is described in [Table 4](#).

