**Table 12 Summary of supportive analyses**

Section	Variable	Imputation method	Analysis	Comment/purpose
15.2.3	Change from baseline to M6	MI (CR)	ANCOVA	Main analysis: MAR model in placebo arm, MNAR (copy reference) in lucerastat arm
15.2.5.1	Responder at M6	Missing = NR (SI)	CMH	Responder if score reduction from baseline at least 30% Missing at M6 = non-responder
15.2.5.2	Change from baseline to M6	MI (CR)	ANCOVA	Impact of not being treated (analysis on FAS)
15.2.5.3	Change from baseline to M6	MI (CR)	ANCOVA	Impact of protocol deviations (analysis on PPS)
15.2.5.4	Change from baseline to M6	MI (CR)	ANCOVA	Impact of use of significant rescue pain therapy Daily scores on days with use of any significant rescue pain therapy substituted by the worst score of subject during the double-blind treatment period
15.2.5.5	Change from baseline to M1, M2, ..., M6	None	MMRM	Mean score by treatment at each month Difference between treatment means at each month Characterization of response over time
15.2.5.6	Responder at M6 if x% reduction	Missing = NR (SI)	CMH	Impact of cut-off for responder definition: responder if score reduction from baseline at least x% (x = 20, 40, 50) instead of 30%
15.2.5.7	Percentage of subjects achieving a x% reduction at Month 6	Missing = NR SI)	Descriptive	Cumulative responder analysis in graph form
15.2.5.8	Improvement according to PGIC (PGIC-DS, PGIC-PS) at Month 6 visit	None	Description, ROC curve	Provides support for clinical relevance of the primary endpoint Using PGIC at Month 6 as an anchor, determines what would be the best cut-off on modified BPI-SF3 change (absolute change or percent change) based on data observed in the study population.
15.2.5.9	Improvement according to	None	Description, ROC curve	Provides support for clinical relevance of the primary endpoint

Section	Variable	Imputation method	Analysis	Comment/purpose
	change in PGIS-D (or PGIS-P) at Month 6 visit			Using change in PGIS-D at Month 6 as an anchor, determines what would be the best cut-off on modified BPI-SF3 change (absolute change or percent change) based on data observed in the study population. Same approach applied separately for change in PGIS-P.

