### 15.2.5.1 Responder analysis

A cut-off of 30% in pain reduction was selected for this responder analysis because this 30% reduction in pain has been shown to represent important improvement in patients with neuropathic pain [Farrar 2001] and it is recommended that the percentages of patients responding with this degree of pain relief be reported in clinical trials of chronic pain treatments [Dworkin 2008]. Based on the evidence found in the literature in non-Fabry patients with neuropathic pain and regulatory guidelines [EMA 2007] (later replaced by [EMA 2017]), a cut-off of 30% was selected.

Using subject responses from the modified BPI-SF3, a response variable (yes/no) for the primary endpoint will be calculated based on a reduction of at least 30% from baseline to Month 6 in the modified BPI-SF3 score of “neuropathic pain at its worst in the last 24 hours”.

Subjects who have a missing modified BPI-SF3 score at Month 6, for any reason, will be considered as non-responders, i.e., the worst possible outcome is assumed.

The Cochran-Mantel-Haenszel (CMH) test stratified by sex and ERT treatment status at screening (treated vs not treated) will be used to test for a difference in the proportions of responders at Month 6 between treatment groups.

The treatment effect (lucerastat vs placebo) will be expressed in terms of the common odds ratio (ORc) and corresponding 95% CI. An  $ORc > 1$  will indicate a response to treatment in favor of lucerastat as compared to placebo.

Homogeneity of the treatment effect across strata will be investigated using the Breslow-Day test.

This analysis will be implemented by the following SAS® code:

```
proc freq;
  tables sex*ertstatus*treatment*response / nocol nopercnt cmhl
  commonriskdiff (cl=newcombe);
run;
```

The Mantel-Haenszel risk (proportion) difference (lucerastat vs placebo) and corresponding 95% CI (stratified by sex and ERT treatment status at screening) will also be provided. The CIs are calculated using the stratified Newcombe method [Yan 2010].

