#### ***15.2.5.7 Empirical cumulative distribution function plots***

Empirical cumulative distribution function (eCDF) plots will be provided for the absolute change from baseline to Month 6 and the percent change from baseline to Month 6 in the modified BPI-SF3 score by treatment group.

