#### ***15.2.5.8 Determination of an anchor-based value for the change in modified BPI-SF3 when using PGIC as external anchor***

In order to assess the clinical relevance in the context of the FD of the cut-off of 30% used in the responder analysis, the change in modified BPI-SF3 at Month 6 will be compared to the classification as responder/non-responder when using the PGIC at Month 6 visit as an external criterion. The methods used will be in line with previous publications in other diseases [Farrar 2010] and an FDA guidance for interpretation of patient-reported outcomes [McLeod 2011]. The two PGIC questionnaires (PGIC-DS, PGIC-PS) will be analyzed separately using the same approach.

These analyses will be conducted on the set of subjects with data available for both the change in modified BPI-SF3 at Month 6 and for the considered PGIC questionnaire at Month 6 visit. The analyses will be conducted on the two study treatment groups combined.

The change in modified BPI-SF3 at Month 6 will be expressed in two different ways: as absolute change from baseline and as percent change from baseline.

The polyserial and Spearman correlation coefficients between the change in modified BPI-SF3 at Month 6 and PGIC at Month 6 visit will be reported with their 95% CI.

This analysis will be implemented by the following SAS® code:

```
proc corr spearman fisher polyserial;  
  with pgicchange;  
  var percentchange;  
run;
```

The confidence limits of the polyserial correlation coefficient will be derived as the coefficient  $\pm 1.96$  multiplied by its standard error. The confidence limits of the Spearman correlation coefficient will be derived using Fisher's z-transformation.

The correspondence between change in modified BPI-SF3 at Month 6 and the PGIC at Month 6 visit will be graphed by displaying the distribution (using box-plots) of modified BPI-SF3 at Month 6 within each PGIC level.

Three different response variables (yes/no), each corresponding to levels of improvement as characterized by the PGIC at Month 6 visit will be examined: "minimally improved" or better (PGIC = 1, 2 or 3); "much improved" or better (PGIC = 1 or 2); or "very much improved" (PGIC = 1).

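### Outside the fixed sequence, the SAP treats a fall to 0 as a missing percent change, log-transforms a rating that can be 0, and omits the protocol's baseline limit on the abdominal-pain responder analysis

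*SAP*

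**What the plan says.** **Percent change.** SAP 14 defines percent change as absolute change over baseline, times 100. For the case "or if baseline greater than 0 and post-baseline equal to 0" it then says "the percent change will be missing", giving as the reason that the log ratio is minus infinity. It continues: "Summary statistics of percentage changes will be derived from the geometric mean of the ratio to baseline". SAP 9.6.1 gives the plain formula for BPI-SF item 5, with no exception for zero.

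**Where percent change in BPI-SF3 is used.** SAP 15.2.5.7 plots the distribution of absolute change and of "the percent change from baseline to Month 6 in the modified BPI-SF3 score by treatment group". SAP 15.2.5.8 and 15.2.5.9 express the change "as absolute change from baseline and as percent change from baseline" for the anchor and ROC work, with the arms pooled, and Tables 13 and 14 report percent change only. Protocol 10.3.2.5 plans a cumulative plot of the share of subjects reaching an x% reduction, with x running from 0 to 100.

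**Item 5.** SAP 15.4.4.1 analyses the change by ANCOVA and repeats it on log-transformed data. It gives no offset or zero rule of its own.

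**Abdominal-pain responders.** Protocol 10.3.3.1 defines the 50% response in subjects with moderate-to-severe abdominal pain at baseline. SAP 15.3.1 gives the same cut-off on the mFAS-GIS without that limit. SAP 15.3.2 does state a baseline limit for the diarrhea responder analysis. SAP 20 lists only changes to subgroups.

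**The concern.** On a 0-10 pain scale, zero is the best result a subject can have. A rule that makes it missing removes subjects because of their outcome. Where the arms are compared, the loss falls more heavily on the arm with more complete resolutions. Where they are pooled, it trims the top of the improvement range that the anchor analyses are meant to describe. These outputs are there to support the clinical relevance of the primary result.

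The third item is different in kind. A responder difference would be reported in a wider population than the protocol defines, including subjects with little abdominal pain to reduce, and the reader of the report would not be told.

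**Working it through.** The plan states no figure that depends on this point, so there is none to reproduce.

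**1. Fall to zero as a percent change**
- SAP 14 and 9.6.1 formula, for any baseline b > 0 and Month 6 value 0: 100 x (0 - b)/b = -100%. The SAP 14 exception turns this into missing.
- The exception exists for the geometric mean: one ratio of 0 makes the geometric mean 0, and (0 - 1) x 100 = -100% for the whole group.
- Biomarkers do not need it, because SAP 9.2.3 and 13 set values below quantification to the limit of quantification.
- In the protocol's cumulative plot, x = 100 can be reached only by a Month 6 score of 0. Under SAP 14 no subject can have a percent change of -100%, so the two texts conflict at that point.
- How often? SAP 9.1 requires at least 4 daily scores for a valid week, and "at least 3 valid weekly scores should be non-missing to derive a valid score for the relevant time period". A Month 6 score of 0 therefore needs at least 3 x 4 = 12 recorded days, all scored 0. That is probably rare.
- Illustration on assumed inputs: a share z of an arm falls to 0 and all others change by -20%. The arithmetic mean is -20(1 - z) - 100z. For z = 2%, 5%, 10% and 15% it is -21.6%, -24%, -28% and -32%. With the zeros removed it is -20% each time.

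**2. Log of item 5**
- Protocol 7.2.2.3 scores the BPI-SF severity items on an NRS-11, so 0 is valid. The entry threshold of 4 (Protocol 4.3) applies to the 4-week average of the modified BPI-SF3, not to item 5.
- A fall from 4 to 1 is kept: ln(1/4) = -1.39, or -75%. A fall from 4 to 0 has no log and is missing. A rise from 0 is also missing. Only 0 to 0 has a rule (ratio 1), and even that subject is lost if log-baseline is the covariate. SAP 15.3.3 specifies that covariate for Gb3; SAP 15.4.4.1 does not say.
- Illustration by simulation, on assumed inputs: baseline mean 5.5, SD 2; change SD 3; scores rounded and held to 0-10. With an assumed mean change (before the limits) of -1 and -3, 13.0% and 28.5% of subjects fall to 0. Dropping anyone with a zero moves the mean absolute change from -0.91 to -0.49 and from -2.50 to -1.82.
- Taking these two cases as two arms, the difference goes from -2.50 - (-0.91) = -1.59 to -1.82 - (-0.49) = -1.33. This shows direction on the absolute scale. It does not predict the trial.

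**3. Abdominal-pain responders**
- SAP 4.1.4 admits a subject to the mFAS-GIS on an average abdominal pain of at least 3 and/or on diarrhea days. Diarrhea-only subjects therefore enter the SAP 15.3.1 analysis without meeting the pain threshold.
- Expected mFAS-GIS: 70% (Protocol 10.5) x 118 randomized (SAP 2) = 82.6, about 83.
- Let d be the share without moderate-to-severe abdominal pain; the documents do not give it. If d is equal by arm and those subjects show no treatment effect, the risk difference is multiplied by (1 - d). For an assumed 20 points: 20 x 0.90 = 18, 20 x 0.70 = 14, 20 x 0.50 = 10.
- d from 10% to 50% of 83 is about 8 to 41 subjects.

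**The case against.** The SAP 14 exception plainly serves the geometric-mean summary. Tables 13 and 14 ask for means, SDs and percentiles, SAP 9.6.1 has no exception, and the absolute-change versions of the plots and anchor analyses are also produced. Removal of resolutions everywhere is thus a literal reading, not a declared intention. That is fair, but the rule is written for the individual value and nothing confines it, so a programmer who follows it would drop them.

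On item 5, the absolute-change ANCOVA stands, and the log version is a second presentation of an exploratory endpoint. That limits the weight of the point but does not supply a zero rule.

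On abdominal pain, the SAP is silent; it does not say that the limit is removed, and it is based on the current protocol. It would be wrong to add that the SAP kept a protocol limit for diarrhea while dropping this one. Protocol 10.3.3.2 only carries the responder analysis over to the stool endpoint, and the explicit diarrhea wording is the SAP's own. The contrast shows no more than that the SAP states a limit where one is meant.

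A reader might also infer from Table 12 that complete resolutions become non-responders, because the row for 15.2.5.7 ("Cumulative responder analysis in graph form") carries the missing-as-non-responder entry. The documents do not support this. The 15.2.5.1 row of the same table ties that entry to missing data at Month 6, and SAP 15.2.5.1 says "Subjects who have a missing modified BPI-SF3 score at Month 6, for any reason, will be considered as non-responders". SAP 15.2.5.6 repeats it. A subject who scores 0 has a Month 6 score and is a responder.

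**Conclusion.** The point holds as a minor one, for supportive and exploratory analyses only. Neuropathic pain, Gb3 and abdominal pain are tested on absolute change, and stool days on ranks of absolute change, so nothing here reaches the primary test or the fixed sequence.

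What stands is three defects of text: an exception in SAP 14 that contradicts its own formula and the protocol's cumulative plot; a log analysis of a scale that includes 0, with exclusion that depends on outcome in a between-arm comparison; and an undeclared omission of a protocol population limit.

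The size of the first two is unknown, because the documents give no frequency of zeros. It is probably small for BPI-SF3, a 4-week average, and could be larger for item 5, a single rating. For the third, the 18, 14 and 10 points rest on an assumed 20-point difference, an assumed share below the threshold, and no effect in those subjects. A subject with baseline pain above 0 but below 3 can still halve the score, so dilution is one scenario and not a certainty.

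**What to change.** - **SAP 14:** code a positive baseline followed by 0 as -100%. Confine the log-ratio rule and the geometric-mean summary to strictly positive variables such as biomarkers and echocardiography measures. Summarize percent change in the 0-10 scores by medians and quartiles or by arithmetic means.
- **SAP 15.4.4.1:** drop the log-transformed ANCOVA of item 5 and rely on the absolute-change ANCOVA already planned.
- **SAP 15.3.1:** restore the limit to subjects with moderate-to-severe abdominal pain at baseline (average NRS-11 of at least 3), or declare and justify the change in SAP 20.

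The cost is a few SAP sentences and small derivation changes before unblinding. No new data are needed, and one exploratory table is lost.
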